Outer Context	What would need to be in place external to [organization] in order for Tula to be made part of your regular service offerings?
Innovation	Knowing what you know about Tula, which needs at [organization] might it fill? What changes could be made to Tula that would improve its ability to meet those needs?
Bridging	What can the Tula team do now that would make it more likely that [organization] would make Tula part of its regular service offerings?

Remuneration. No remuneration will be provided to these participant groups.

Unanticipated Events

Should any unanticipated problems arise, the research team will work with the HS IRB to address the problems according to posted IRB guidance. The following is intended to further clarify some possible scenarios.

Protocol

HS IRB #2019-0337
Version 5. 10/17/19
Version 6. 04/07/20
Version 7. 10/09/20
Version 8. 01/26/21
Version 9. 08/18/21
Version 10. 07/13/23

If a patient (1) stops receiving treatment at one of the participating clinics or (2) becomes incarcerated, the patient will remain enrolled in the study and their circumstances will be documented by the UW study coordinator.

In the first case, the patient would continue to complete surveys and use Tula if applicable per the study protocol.

In the second case, no research activities would occur during the time of incarceration. If the patient is released during the study period, s/he can contact the study coordinator to continue in the study, if s/he would like. The reason for any missed data will be documented.

Subjects may sometimes use Tula inappropriately. Discussion group moderators will review and delete any discussion board messages deemed inappropriate (i.e., those containing nudity, threats, racism, and bigotry). A research staff member will then follow up with the author of the inappropriate content.

Cases in which a subject has ongoing borderline behavior will be evaluated individually and the subject may be removed from study if the research team feels it is in the best interest of the subject as well as the others in the study.

Privacy and Confidentiality

To mitigate the risk of patient breaches of confidentiality, all patient subjects will choose a username when they create an account. A list of patient subject usernames will be kept by the research team PI and stored in a secure, limited access, password-protected file service on HIP servers, which are located in the University Bay Office Building. Any hard copy identifying information will be stored in a locked cabinet. Other identifiable data entered into Tula by the patient subject will be removed by [name], the CHESS data security officer, before it can be accessed by the research team. [name] acts as an honest broker at CHESS for the patient data collected through Tula; the study team will also request that [name], SMPH honest broker, confirm that the dataset is de-identified before it is uploaded to Google Drive. During account creation, the Tula system will assist patients in choosing a username and password to log in to the Tula system. Patients will be instructed not to use their real names or other identifying information as a username and will be made aware of the potential dangers of divulging confidential information (e.g. real names or telephone numbers).

Subjects in the clinically integrated group who decide to share their Tula data with health providers may choose to stop sharing at any time. Subjects will be asked whether or not they want to share data with the health coach each time they enter data in Tula, and have the option to stop sharing their data permanently and retrospectively by going to the app privacy settings and selecting the option “do not allow others to see my data.” In this case, the health coach would not see anything about the patient’s participation and only the research team would have access to the subject’s data.

Protocol

HS IRB #2019-0337
Version 5. 10/17/19
Version 6. 04/07/20
Version 7. 10/09/20
Version 8. 01/26/21
Version 9. 08/18/21
Version 10. 07/13/23

No data collected by Tula will be entered into patients' electronic medical record or affect the legal medical record.

Clinician interview data will be recorded using secure encrypted, password-protected recording devices. The recording will be transferred to the Health Innovation Program password-protected servers as soon as possible and deleted from the recording device. Recordings will be transcribed, coded, and removed of all identifying information. Once the recording is transcribed, the recording will be deleted from the server.

Participant interviews will be audio recorded and transcribed by a HIPAA approved service from the Wisconsin Surgical Outcomes Research program. All data will be coded, de-identified, and assigned a study ID. Any identifying information will be stored separately in a password-protected server as soon as possible. Once the recording is transcribed and the transcript is spot checked for accuracy, the recording will be deleted from the server.

Potential Risks

The main risks are the potential for subjects to receive and act on bad information or misinterpret accurate information, and the potential that confidentiality of the subjects' records will be breached. More specifically:

- Depending on the method of recruitment and how a participant learns about the study, it is possible some participants may feel compelled or obliged to participate because the recommendation comes from a person deemed by the participant to be in an authority position. Participants may be concerned about maintaining their standard of care. Every effort will be made to clarify to participants that their care will not be affected whether they participate or not.
- Through screening processes, which derives its questions from AUDIT and DSM-5 questionnaires, individuals' responses may suggest symptoms of an undiagnosed severe case of alcohol use disorder. This may be upsetting to them, especially in the context of not being able to take advantage of the resources/support provided in Tula. Like all participants who screen ineligible, these individuals will receive either an email or a phone call, per the communication preference they selected during the screening survey, informing them that they are not eligible for this study. They will be encouraged to talk with their primary care provider about their alcohol use. Patients do not have to follow through on the recommendation to receive treatment.
- Patient subjects in the clinically integrated group could be disclosing possibly stigmatizing alcohol use data to the health coach that may affect treatment at UW Health. We will mitigate this risk by giving the patient subject the option of choosing which data, if any, to share with the health coach. Consent forms will make it clear that any data that the patient does not want to share will not be available to the health coach and by extension any providers within the UW Health system. Furthermore, Tula data will not be entered into the patient's electronic medical record.

Protocol

HS IRB #2019-0337

Version 5. 10/17/19

Version 6. 04/07/20

Version 7. 10/09/20

Version 8. 01/26/21

Version 9. 08/18/21

Version 10. 07/13/23

- Tula could provide inaccurate or harmful information. The information will carefully vetted by experts from the clinics ([name]), the study team, and UW CHESS's Steering Committee. Network communications between subjects will be monitored. Inaccurate or harmful statements will be addressed by the Tula moderator. Additionally, messages exchanged within the Tula support groups will be monitored to make sure the information is accurate and that study participants are using the system for its intended purpose.
- There could be a breach of confidentiality that could result in disclosure of research data outside of the study team. This could carry economic or legal risks for subjects. To prevent this, all subjects will be assigned a de-identified code number (separate from the username). These lists will be kept in a locked spreadsheet on the HIP servers, and will not be shown to anyone except study staff. Data collected from smartphone use files will have the name removed and the code number attached by the research team study coordinator. Interviews will be conducted by research staff trained in human subjects training.
- There is risk that information provided in Tula will be used to the detriment of the subjects. Particular sources of risk include email and newsgroups, as well as Tula communications written within the discussion groups or personal profiles. Patients will create an account with a username and password to use on Tula. They will be instructed to not use their real name as a username and will be warned of the potential dangers of divulging confidential information (e.g. real names or telephone numbers). Patients will also be asked in the informed consent and given directions to set up a passcode on the phone to protect their information in the event someone else finds the phone.
- There may be a stigma attached to using Tula. There are times and contexts when notifications of weekly or monthly surveys draws unwanted attention. In these instances, study participants can set their smartphones to vibrate so they are subtly prompted to complete their weekly check-in survey, and they can also have the option to prompt the system to remind them later for a check-in at a more appropriate time.
- Participants may send messages when moderators cannot respond quickly. Offering features could produce over reliance on Tula to provide support during periods of distress. Study participants will be told that the moderator of their discussion group will make every effort to follow-up on their messages for support. If the moderator is not immediately available, the app will let the participant know that a moderator is unavailable and if they need immediate assistance they should contact their UW health clinic. To maintain a separation between research and clinical activities, members of the study team will not forward patient messages to the central desk of their UW health clinic.

Additional risks may include:

- Learning about sensitive issues, such as excessive alcohol use, while using the Tula app may cause anxiety, distress, embarrassment, or feelings of sadness. However, patient subjects do not have to answer any questions that they don't want to answer.
- The research team will be collecting information on how the smartphone is used and may discover behavior that raises concern about harm to self or others. If we see anything that

Protocol
HS IRB #2019-0337
Version 5. 10/17/19
Version 6. 04/07/20
Version 7. 10/09/20
Version 8. 01/26/21
Version 9. 08/18/21
Version 10. 07/13/23

suggests that patient subjects or others face imminent risk of harm, we will contact appropriate others to intervene (e.g. the police). Individuals will be told this during informed consent.

- All clinicians who are interviewed will be told that they do not have to answer any questions they do not wish to answer. The study team will have any identifying information coded and removed from transcripts. The code key will be kept separate from the transcripts in a locked cabinet. After transcripts are made from recordings of the interviews, the recordings will be destroyed.

To further protect subject confidentiality, all studies funded by the National Institute of Health are issued a Certificate of Confidentiality which prevents investigators and institutions from being required to release identifiable subject information.

Data Storage and Protection

CHESS and HIP servers are separate servers. All data collected through the Tula app will be stored on CHESS password-protected servers. CHESS programmers will create de-identified data exports and uploaded to a UW-sponsored Secure Box where it can be accessed for statistical analyses by UW study members and [name] of the University of Kentucky. All data collected outside of Tula (interview transcripts, code keys, etc.) will be stored on HIP password-protected servers.

When all study activities are complete, audio recordings, participant IDs, and other identifiable information will be destroyed; only the de-identified code will remain. The study team does not intend to retain data collected for this study for purposes not described in this application.

Table 2. Data and location of storage.

Data	Location
Subject intake	CHESS servers, Google Drive
Subject demographics	CHESS servers, Google Drive
Subject electronic consent	CHESS servers, Google Drive
De-identified Tula surveys	CHESS servers, Google Drive
De-identified Tula use data	CHESS servers, Google Drive
Interview data	HIP servers
Initial screening data	Qualtrics
Any other hardcopy records	Locked file cabinet

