2.0 STUDY OBJECTIVES

This project proposes a hybrid type II effectiveness/implementation trial that will test the effect on risky drinking patterns and quality of life associated with patient use of an mHealth system under a variety of implementation

Primary Aim:

Detect the effectiveness of interventions by assessing the difference in self-reported risky drinking patterns and quality of life between subjects in the three study groups (self-monitoring, peer-supported, and clinically integrated groups).

Secondary Aims:

Because the study is designed to investigate both the effectiveness of Tula in primary care and the comparative effectiveness of different implementation strategies, the following secondary goals complement study's primary aims:

- Understand the significance clinician monitoring has on alcohol use interventions and patient outcomes.
- Calculate the costs of health system use for each group.
- Develop an mHealth reimbursement strategy prototype using CMS billing codes in the clinically integrated group.
- Understand the degree to which sex moderates the intervention outcomes among Tula users.
- Understand the degree to which patient competence, relatedness, and autonomous motivation (three tenets of self-determination theory) mediate the intervention effect in the Tula groups.
- Assess the dose/response relationship between Tula use and degrees of outcomes
- Understand the impact clinician monitoring has on AUD treatment.
- Qualitatively assesses clinician engagement and clinic needs to further refine Tula and its associated integration for future implementation and dissemination.

Sub-aim:

- Understand the relationship between pain and alcohol consumption after the 3-month active intervention.

Study Coordination

The Implementation Science and Engineering Lab is the coordinating site for this study. The UW study coordinator will oversee all activities at participating UW Health recruitment sites. Activities include:

- developing site-specific recruitment and data collection processes that meet study objectives;
- training the health coaches on protocol procedures prior to the start of recruitment and continuous monitoring to assure compliance with the protocol and human subjects regulation;
- communicating with site staff via regular conference calls to monitor progress, inform of protocol

Protocol

HS IRB #2019-0337
Version 5. 10/17/19
Version 6. 04/07/20
Version 7. 10/09/20
Version 8. 01/26/21
Version 9. 08/18/21

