HS IRB #2019-0337
Version 5. 10/17/19
Version 6. 04/07/20
Version 7. 10/09/20
Version 8. 01/26/21
Version 9. 08/18/21
Version 10. 07/13/23

Following randomization, study staff will call the individual to notify them which group they are in and explain what is required of them.

Patients will need to install just one version of Tula because the features patients have access to will be modified according to the randomization group.

Patients in all groups will be asked during the consent process to allow monitoring of their Tula usage by the research team to determine which parts of Tula are most helpful; patients randomized to the clinically integrated group will have the option to share information from Tula with the health coach at UW Health. All data shared from patients to the UW Health health-coach will be initiated by the patient.

Remuneration. Participants who complete the screening survey will receive a \$10 digital Amazon.com Gift Card in the email sent to communicate their eligibility status, regardless of their eligibility.

In all recruitment scenarios, subjects will be told the study incentives (\$10 for completing the eligibility screen; up to \$250 for enrollment and participation in the study) and how to earn them in the study:

- complete baseline measures in the Tula app, for which subjects will be paid \$30;
- complete weekly surveys for the first 12 weeks of the study, for which subjects will be paid \$10 per completed week (all groups);
- complete 4 quarterly surveys (between months 3-12), for which participants will be paid \$20 each;
- earn a bonus of \$20 for completing all surveys

Incentives will be distributed monthly to subjects by digital gift code. If subjects prefer to receive incentives via e-mail, they must grant the study team permission to use their email address for this purpose; otherwise, monthly incentives will be delivered securely through the in-app communication tool (private message). Subjects will be notified of this information when they formally consent to participate in the study

For the participant interviews, each participant will receive a \$50 gift card in remuneration for their time.

Clinic Staff

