Patient and clinician decision making	Value and decision framing survey	Patient/ clinician survey	9	Patient: Pretest, 12 months Clinician: during interview at month 36
Mediators				
Relatedness	CHESS Bonding Scale ^{48,65}	Patient survey	5	
Competence	Perceived Competence Scale	Patient survey	4	0, 3, 6, 9, 12 mo.
Autonomous motivation	TSRQ ⁶⁶	Patient survey	6	
Tula use (patients)	Number of days used, number of pages viewed	Server log files	NA	Continuous
Moderators				
Patient characteristics	Race, ethnicity, gender, age	Patient survey	NA	Pretest

Protocol

HS IRB #2019-0337
Version 5. 10/17/19
Version 6. 04/07/20
Version 7. 10/09/20
Version 8. 01/26/21
Version 9. 08/18/21
Version 10. 07/13/23

All survey data collected through Tula is housed on CHESS servers then exported to the UW sponsored Google Drive folder for statistical analyses.

Screening survey: People interested in participating in the study will be directed to take a Qualtrics screening survey hosted on the Web to determine if they are eligible to participate in the study.

Baseline survey. After patient subjects are enrolled in the study, they will be asked to take a baseline survey consisting of demographic questions, medical service utilization, quality of life, a modified version of the Brief Alcohol Monitor, the CHESS bonding scale, the alcohol competence scale, the TSRQ, and the value of Tula. Data from the screening survey will be used as baseline data for the AUDIT, AUD DSM-5, and timeline follow-back. Two additional questions related to the impact of COVID-19 on participants' physical and mental health will be added to the quality of life measures. These questions will operate on a 5-point Likert scale and will be included across all CHESS studies. (See supporting document "4.6.20 Global Health Scale v1.3_COVID.docx").

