6.0 MEASUREMENT OF EFFECT

All scales have good psychometric properties with similar populations. Listed below are the factors to be measured and measurement instruments.

Intake only. Study staff will confirm patient eligibility via patients' UW Qualtrics screening surveys . Patients report demographics (biological sex, race, ethnicity, age, education).

Protocol
HS IRB #2019-0337
Version 5. 10/17/19
Version 6. 04/07/20
Version 7. 10/09/20
Version 8. 01/26/21
Version 9. 08/18/21
Version 10. 07/13/23

Drinking and quality of life. Patients will be asked to take surveys administered via the Tula app (see Table 1 for frequencies). Patients will be asked to report on their drinking using the 7-day timeline follow-back^{58,59} survey. Patients will also take the PROMIS Global Health⁶⁰ survey (10 items) to assess patient self-reported quality of life and a modified version of the Brief Alcohol Monitor⁶³ survey (10 items) to assess their risk and protection factors for problematic alcohol use. Alcohol use disorder severity (AUD scale,⁶⁴ 11 items; AUDIT, 10 items; 7-day timeline followback, 5 items) will be assessed at baseline and once every 3 months.

Mediators. Self-determination theory constructs will be assessed (see Table 1 for frequencies) via the Tula app as follows:

- Competence – Perceived Competence Scale (4 items)
- Relatedness – CHESS Bonding Scale^{65,66} (5 items)
- Autonomous motivation – revised Treatment Self Regulations Questionnaire⁶⁷ (6 items)

Tula use. Tula use is collected in time-stamped log files and includes when a patient accessed Tula, the services used, duration of service use, pages viewed, messages posted and received, and content of messages. Tula use will be used to measure dose of intervention received for dose/response analyses. Patients will be asked to take a survey about their value of Tula at baseline and 12 months.

Healthcare utilization. Healthcare utilization will be collected from the self-reported medical services utilization form⁶¹ (6 items; see Table 1 for frequency).

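### The Tula dose measure does not exclude the paid quarterly outcome surveys taken in the app, so dose is partly tied to having outcome data

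*Combined protocol and SAP*

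**What the plan says.** Section 2.0 lists as a secondary aim: "Assess the dose/response relationship between Tula use and degrees of outcomes". Table 1 in Section 5.0 has one row for patient Tula use, placed under mediators, taken continuously from server logs and measured as "Number of days used, number of pages viewed". Section 6.0 states its purpose: "Tula use will be used to measure dose of intervention received for dose/response analyses". The same paragraph describes a wider log, including "the services used, duration of service use, pages viewed, messages posted and received, and content of messages", but does not say which of these elements form the dose. Section 8.0 contains no dose/response model that would settle it.

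On the surveys, Section 6.0 says: "Patients will be asked to take surveys administered via the Tula app". Section 4.0 (Remuneration) pays for them: "complete baseline measures in the Tula app, for which subjects will be paid" (USD 30); "complete weekly surveys for the first 12 weeks of the study, for which subjects will be paid" (USD 10 each, all groups); four quarterly surveys at USD 20 each; and a USD 20 bonus for completing everything. Section 5.0 puts the timeline follow-back and the quality-of-life scale in the quarterly surveys at months 3, 6, 9 and 12.

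Two further statements limit the point. Section 1.0 describes the weekly survey as part of the Tracker, which all three groups receive. Section 5.0 starts the capture of use data at randomization, after the run-in in which the baseline survey and the first weekly survey are completed.

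**The concern.** A dose variable should record exposure to the intervention. The quarterly surveys are measurement only, yet each one completed takes at least one app day and some page views. Under the Table 1 definition, the same act supplies an outcome and adds to the dose.

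If participants who are drinking less are also more likely to keep completing surveys, part of a dose/response gradient could come from survey completion rather than from Tula. Weekly surveys are requested only in the three-month active period. From then on, the quarterly surveys are the only survey task asked of participants, so a light user's later days of use may be largely data collection.

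**Working it through.** **1. Payment schedule.** Inputs are from Section 4.0: 30 + 12×10 + 4×20 + 20 = USD 250, which matches the stated maximum. Of this, 120 + 80 + 20 = USD 220 (88%) is tied to surveys after baseline. The motive to open the app for surveys alone is therefore real in every group.

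**2. Survey days that can enter the log.** The run-in surveys precede use capture, so the baseline survey drops out and 11 to 12 weekly surveys remain, plus 4 quarterly. A participant who completes every survey and opens Tula for nothing else could log 15 to 16 days over 12 months, fewer if surveys share a day. Of these, 4 are pure measurement (4/16 = 25% to 4/15 = 27%) and 11 to 12 are Tracker use. Only the month-3 survey touches the active period.

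For a participant who completes every survey and has *o* other days of use, the quarterly share is 4/(15+*o*) to 4/(16+*o*):

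| Other days | Quarterly share of days used | All-survey share |
|---|---|---|
| 5 | 19–20% | 75–76% |
| 10 | 15–16% | 60–62% |
| 20 | 11% | 43–44% |
| 40 | 7% | 27–29% |

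The documents give no expected level of Tula use in this trial, so *o* is an assumption.

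**3. Share of the variance in days used.** Let *v* be the SD of all other use days, assumed independent of quarterly completion. The share due to quarterly surveys is V/(V+*v*²). A count from 0 to 4 has variance at most (4/2)² = 4, reached when half the participants complete all four and half complete none.

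- *v* = 4: 4/(4+16) = 20%
- *v* = 8: 4/(4+64) = 6%
- *v* = 16: 4/(4+256) = 1.5%

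If only participants with a month-12 outcome are analysed, that survey adds the same day for all of them and at most three quarterly days can vary. The variance cap is then (3/2)² = 2.25, and the shares are at most 2.25/18.25 = 12%, 2.25/66.25 = 3.4% and 2.25/258.25 = 0.9%.

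**4. Link between dose and outcome completeness.** A simulation of 200,000 participants used these assumptions, none of which is in the documents as such: one completion propensity per person, averaging about 77%, drives both weekly and quarterly surveys; there are 11 weekly and 4 quarterly surveys, each on its own day; other days are negative binomial with size 1 and independent of completion. The correlation of days used with the number of quarterly surveys completed was:

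| Mean other days | All surveys counted | Quarterly excluded | All surveys excluded |
|---|---|---|---|
| 5 | 0.46 | 0.31 | 0.00 |
| 10 | 0.27 | 0.18 | 0.00 |
| 20 | 0.15 | 0.09 | 0.00 |
| 40 | 0.08 | 0.05 | 0.00 |

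Excluding the quarterly surveys removes roughly a third of the link. The rest runs through weekly surveys, because the simulation lets one propensity drive both. That is why a second version of the dose is worth reporting.

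Pages viewed cannot be sized, since the documents do not give the number of pages in any survey.

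**The case against.** The strongest objection is that the plan never says surveys are counted. The Table 1 row is a short summary, and Section 6.0 describes a richer log without limiting dose to days and pages. This is fair: inclusion is read from a definition that has no exclusion. But days and pages are the only measures tabulated for Tula use, and nothing commits the analyst to filter them. That the log would permit a filter does not mean that one is planned.

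The second objection is that the weekly survey is intervention content. It is a Tracker feature for all groups, and in the clinically integrated group shared responses feed the health coach's dashboard. This stands. A reader might infer that all 15 to 16 paid log-ins are false dose, or that up to half the variance in days used is survey compliance. The latter requires treating weekly surveys as non-dose and assuming an SD of 4 for survey days: 16/(16+*v*²) = 50%, 20% and 6% for *v* = 4, 8 and 16. The documents do not support either reading.

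A reader might also infer that the self-monitoring group is credited with a dose it did not receive. That fails too: the group receives the static content and the weekly tracking, so recording use there is accurate apart from the quarterly surveys.

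Third, the bias is conditional. A participant without an outcome at a visit adds nothing at that visit, and for those with one, that visit's survey adds a day to everyone. A spurious gradient needs completion of the other surveys to track drinking. This is correct, and the documents neither establish nor exclude it.

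**Conclusion.** The point holds in a limited form. The dose as tabulated does not exclude the paid quarterly outcome surveys, so it counts some data collection as exposure and is partly tied to outcome completeness. The clear contamination is at most 4 days per participant plus the survey pages. It amounts to at most about 20%, 6% and 1.5% of the variance in days used, for an assumed SD of other use of 4, 8 and 16 days. Those caps rest on independence between other use and quarterly completion, and on each survey taking its own day.

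Counting the weekly survey is defensible, although it is paid and can add a further 11 to 12 days after randomization.

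The consequence is confined to the secondary dose/response analysis. A reader might infer that the as-treated, per-protocol or complier-average estimates in Section 8.0 are also affected. That would follow only if they define compliance by this measure, which the plan does not state. The intention-to-treat comparison is untouched. This is a minor point that is cheap to settle before analysis.

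**What to change.** In Table 1 (Section 5.0) and the Tula use paragraph of Section 6.0, define the primary dose as days used and pages viewed after randomization, excluding quarterly survey pages and any day on which only a quarterly survey was opened. The log field for services used should allow this split.

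Add a pre-specified sensitivity version that also excludes weekly survey pages and days on which only a survey was opened. Reporting both shows how far any gradient depends on survey completion.

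The cost is a few sentences and a log-file filter, with no new data and no added burden on participants. The small downside is that the sensitivity version drops a self-monitoring component that is part of the intervention, which is why it should not be the primary definition. Settling the definition now also avoids choosing one after results are seen.
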